8. RESEARCH QUESTION AND OBJECTIVES

The objectives of this non-interventional study are to examine patient characteristics, usage and effectiveness of abrocitinib in adult patients with moderate to severe AD who have been chosen to start treatment with abrocitinib in a real-world context such as dermatological practices in Germany. The following factors will be considered, if collected as part of the medical routine:

Research Questions:

Primary Objective:

The primary objective of this non-interventional study is to describe the efficacy of abrocitinib treatment.

- In terms of patients achieving a clear or almost clear AD morphology 3 months after first prescription of abrocitinib based on the IGA Questionnaire.
- In terms of patients achieving a \geq 75% improvement in lesion extent and severity 3 months after first prescription of abrocitinib based on the EASI-75.

Secondary Objectives:

The secondary objectives of this non-interventional study are:

- To document the efficacy of abrocitinib treatment based on physicians' assessment:
 - Physician's global assessment of AD: Scoring Atopic Dermatitis (SCORAD), EASI, IGA change to baseline.
- To document the efficacy of abrocitinib treatment based on patients' assessment:
 - Patient's global assessment of AD: change in quality of life, Dermatology Life Quality-Index (DLQI), Patient Oriented Eczema Measure (POEM);
 - Patient's assessment of anxiety and depression: Hospital Anxiety and Depression Scale (HADS);
 - Patient's assessment of pruritus: Peak Pruritus Numeric Rating Scale (PP-NRS), mean-NRS and sleep: Medical Outcomes Study Sleep (MOS) Scale;
 - Meeting the patient's expectations (change in the Patient Benefit Index [PBI]) with regard to medical treatment;
 - Number of days with topical-treatment use (topical corticosteroid (TCS)), topical calcineurin inhibitor (TCI);
 - Number of days with emollients use.

Explorative objectives:

The explorative objectives of this non-interventional study are:

- To document patient characteristics and treatment decisions in terms of:
 - Patient characteristics, clinical history, comorbidities and previous therapies;
 - Reasons for starting/ending treatment with abrocitinib, concomitant treatments;
 - Dosage and actual use of abrocitinib as assessed by the treating physician and the patient.
- To assess the safety in terms of adverse and serious adverse events that will occur in the observation period. Severity categories (mild, moderate and severe) of adverse events will be assessed based on investigator's assessment (when applicable).

9. RESEARCH METHODS

9.1. Study Design

This prospective, single-arm, multi-center, observational non-interventional study in Germany does not interfere with the current routine practice of the treating physician. All treatment decisions, types and timing of disease monitoring, diagnostic or other medicinal procedures are at the discretion of the treating physician and patients and are not influenced or affected by the participation in this non-interventional study.

All assessments described in this protocol are performed as part of normal clinical practice or standard practice guidelines for the patient population and healthcare provider specialty in the countries where this non-interventional study is being conducted. There will be no additional diagnostic or monitoring procedures that are outside the routine clinical practice.

This is a 60-month, prospective, non-interventional, multicenter study to evaluate the effectiveness, usage and patient characteristics of abrocitinib in patients with moderate to severe AD in a real-world setting.

Eligible patients will be followed up for 12 months from the date of enrollment. Patients who are switched from abrocitinib therapy to other therapies continue to be observed. Patient documentation is expected quarterly as per standard clinical practice.

Strength of this non-interventional study is the observation of drug prescription and follow-up visits in a daily medical care setting. Therapeutic strategies, patient selection and frequency of patient follow-up are decided by the treating physician.

9.1.1. Endpoints

Primary Endpoints:

- a. Response based on achieving the **IGA** of clear (0) or almost clear (1) (on a 5-point scale) at month 3.
- b. Response based on achieving the **EASI-75** at month 3.

Secondary Endpoints:

Physician's global assessment of efficacy parameters (assessed at all visits [except for month 3 for a. and b.]):

- a. Response based on achieving the **IGA** of clear (0) or almost clear (1) (on a 5-point scale).
- b. Percentage of patients with EASI-75 response compared to baseline.
- c. Response based on achieving the EASI-90.
- d. Response based on achieving the **IGA** of clear (0) or almost clear (1) and a reduction from baseline of ≥ 2 points.
- e. Percentage change of **IGA** compared to baseline.
- f. Percentage change of **SCORAD** compared to baseline.
- g. Absolute **EASI** values over time.
- h. Percentage change of EASI compared to baseline.
- i. Absolute change of **IGA** compared to baseline.

Patient's assessment of efficacy and quality parameters (assessed at all visits):

- a. Response based on achieving at least 4 points improvement of Pruritus **NRS** from baseline.
- b. Change of Peak-Pruritus NRS over time.
- c. Change of **POEM** from baseline.
- d. Change of MOS from baseline.
- e. Change of DLQI from baseline.

- f. Change of HADS from baseline.
- g. Change of EuroQol five-dimensional-five level (EQ-5D-5L) from baseline.
- h. Patient's satisfaction with treatment measured by PBI.
- i. Patient's expectation of treatment measured as PBI at baseline.
- j. Number of days with topical-treatment use (TCS, TCI).
- k. Number of days with emollients use.

Explorative Endpoints:

Treatment characteristics (assessed at all visits):

- a. Concomitant treatments.
- b. Tolerability of abrocitinib and reasons for discontinuation.
- c. Dosage of abrocitinib.
- d. Compliance with abrocitinib treatment.

Patient characteristics assessed at baseline visit only (except for c., f., g., and h. with additional assessment at subsequent visits):

- a. Demographic data of patient (age, sex, weight, occupation, alcohol/smoking, family history).
- b. Clinical history of AD treatment before non-interventional study start.
- c. Comorbidities of interest (atopic diseases, malignancies, cardiovascular diseases, alopecia areata, prurigo nodularis, hand eczema). If baseline visit had a positive anamnesis for the following: (allergic) asthma, (allergic) rhinitis, polyposis nasi, chronic hand eczema, prurigo nodularis and alopecia areata, a qualitative outcome assessment will be done (ie, assessment of investigator if comorbidity improves during abrocitinib therapy).
- d. Previous therapies and reasons for termination of previous treatments.
- e. Reasons for starting treatment with abrocitinib.
- f. Number of AD flares one year before start of treatment with abrocitinib and during observational period.

- g. Number of absent days at work/study caused of AD one year before start of treatment with abrocitinib and during observational period.
- h. Number of AD hospitalizations in the observation period and one year before start of treatment with abrocitinib.

[figure not shown]
Documentation of safety:

- a. Safety: incidence of adverse events and serious adverse events.
- b. Severity of adverse events (when applicable) (as assessed by the investigator according to the following categories:
 - Mild: Does not interfere with the patient's usual function.
 - Moderate: Interferes to some extent with the patient's usual function.
 - Severe: Interferes significantly with the patient's usual function.

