Based on the collected patient characteristics (ie, severity/duration of disease, pretreatment, comorbidities) and the heterogeneity of patient profiles encountered in a real-world setting, potential predictors of response and prognostic factors for an optimal treatment can be identified and on some of them shall be further elaborated. Hand eczema with its atopic subtype²⁰ already has a strong association with atopic dermatitis.²⁰ For instance, with atopic dermatitis and hand eczema, both, the skin barrier dysfunction associated with filaggrin mutations, is relevant.^{21,22} The treatment of hand eczema is quite challenging, but antiinflammatory treatment is important;^{20,23} including JAK inhibition as an interesting new therapy approach.^{23,24} The association of AD and asthma is well established.²⁵ It is now recognized that type 2 cytokines, like IL-4, IL-5 and IL-13, play an important pathophysiological role. ²⁶ Successfully conducted clinical trials with dupilumab in patients with uncontrolled persistent asthma²⁶ and moderate-to-severe uncontrolled asthma²⁷ resulted in the end with a market authorization of dupilumab as add-on maintenance treatment for severe asthma with type 2 inflammation in the European Union. 11 Also allergic rhinitis and polyposis nasi, as atopic morbidities, are driven by type 2 inflammation, ²⁸ resulting in market authorization for dupilumab in the European Union for chronic rhinosinusitis with nasal polyposis. 11 Also in alopecia areata, clinical trials with JAK inhibition were conducted successfully^{29,30} with baricitinib gaining market authorization in the European Union.³¹ Prurigo nodularis and AD share JAK inhibition as a same treatment target (binding of IL-31 to its respective receptor^{32,33} mediated through a JAK1 and JAK2 signaling pathway³⁴) showing efficacy against pruritus.³³ Consequently, the impact of adequately treated AD with abrocitinib on comorbidities of interest, such as (allergic) asthma, (allergic) rhinitis, polyposis nasi, chronic hand eczema, as well as other commonly associated comborbidities, like prurigo nodularis^{32,35} and alopecia areata, ^{36,37} shall be assessed. Above shown information will help to draw inferences and optimize future therapy with abrocitinib and its clinical management.

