9.2.3.2. Schedule of Activities

The recommended schedule of activities table provides an overview of the visits that may be documented. Refer to Section 9.2.4 Assessments section of the protocol for detailed information on each documentation and assessment. As this is a non-interventional study none of these visits are mandatory and every visit should be scheduled according to clinical practice. According to clinical practice the HCP may schedule additional visits to those listed on the schedule of activities, in order to conduct evaluations or assessments required to protect the well-being of the patient.

Table 1. Recommended Schedule of Activities

Study period based on	Baseline	Month	Month	Month	Month	Month
routine visits	(Enroll ment)	1	3	6	9	12 End of Study (EoS)
Visit Number	1	2	3	4	5	6
Informed consent	X					
Inclusion/exclusion criteria	X					
Demographic data of patient (age, sex, weight, height, ethnicity, smoker/non- smoker, education, occupation, alcohol consumption, insurance type)	X					
Family history of atopic diseases	X					
Clinical history (Herpes simplex, eczema herpeticum, herpes zoster)	X					
Renal and/or liver impairment	X					
Vaccination status (Herpes zoster, Covid-19, Influenza, Varicella)	X					X
Age at initial diagnosis of AD	X					
Previous treatments for diagnosed AD	X					
Current comorbidities of interest (atopic diseases, malignancies, cardiovascular diseases)	X					
If positive anamnesis at baseline exists: Improvement of asthma symptoms from baseline						X

Study period based on routine visits	Baseline (Enroll ment)	Month 1	Month 3	Month 6	Month 9	Month 12 End of Study (EoS)
If positive anamnesis at baseline exists: Improvement of allergic rhinitis symptoms from baseline						X
If positive anamnesis at baseline exists: Improvement of polyposis nasi symptoms from baseline						X
If positive anamnesis at baseline exists: Improvement of alopecia areata from baseline						X
If positive anamnesis at baseline exists: Improvement of prurigo nodularis from baseline						X
If positive anamnesis at baseline exists: Improvement of hand eczema from baseline						X
Number of flares during the last 12 months (first visit) and since the last visit (regardless of Abrocitinib treatment status*)	X	X	X	X	X	X
Number of hospitalizations due to AD during the last 12 months (first visit) and since the last visit (regardless of Abrocitinib treatment status*)	X	X	X	X	X	X

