9.2.4.10. Safety

All adverse events (AEs) that will occur during the observation period will be documented. For more information, please refer to Section 11. At the final visit or if a patient discontinues with abrocitinib, the healthcare professional (HCP) will be asked to assess the general tolerability of the treatment with abrocitinib and the reasons for discontinuation (intolerability or lack of efficacy) will be analyzed. When applicable severity categories (mild, moderate and severe) of adverse events will be assessed.

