Clinical history (Herpes simplex, eczema herpeticum, herpes zoster)	X					
Renal and/or liver impairment	X					
Vaccination status (Herpes zoster, Covid- 19, Influenza, Varicella)	X					X
Age at initial diagnosis of AD	X					

Study period based on routine visits	Baseline	Month	Month	Month	Month	Month
routine visits	(Enroll ment)	1	3	6	9	12
						End of Study (EoS)
Previous treatments for diagnosed AD	X					
Current comorbidities	X					
If positive anamnesis at baseline exists: Improvement of asthma symptoms from baseline						X
If positive anamnesis at baseline exists: Improvement of allergic rhinitis symptoms from baseline						X
If positive anamnesis at baseline exists: Improvement of polyposis nasi symptoms from baseline						X
If positive anamnesis at baseline exists: Improvement of alopecia areata from baseline						X
If positive anamnesis at baseline exists: Improvement of prurigo nodularis from baseline						X
If positive anamnesis at baseline exists:						X

[figure not shown]
Study period based on routine visits	Baseline (Enroll	Month	Month	Month	Month	Month
routine visits	ment)	1	3	6	9	12
						End of Study (EoS)
Improvement of hand eczema from baseline						
Number of flares during the last 12 months (first visit) and since the last visit (regardless of abrocitinib treatment status*)	X	X	X	X	X	X
Number of hospitalizations due to AD during the last 12 months (first visit) and since the last visit (regardless of abrocitinib treatment status*)	X	X	X	X	X	X
Number of absent days at work/study due to AD one year before start of treatment with abrocitinib (first visit) and since the last visit (regardless of abrocitinib treatment status*)	X	X	X	X	X	X
Reasons for start of therapy with abrocitinib	X					
Reasons for discontinuation of therapy with abrocitinib		X	X	X	X	X

Study period based on	Baseline	Month	Month	Month	Month	Month
routine visits	(Enroll ment)	1	3	6	9	12
						End of Study (EoS)
Compliance with abrocitinib treatment		X	X	X	X	X
Dosage of abrocitinib used	X	X	X	X	X	X
Reasons for prescribed dosage	X	X	X	X	X	X
Type and results of laboratory check controls	X	X	X	X	X	X
Adverse events		X	X	X	X	X
Concomitant treatment AD specific (type and dosage)	X	X	X	X	X	X
Number of days with topical- treatment use (TCS, TCI) & days with emollients use three months before start of treatment with abrocitinib (first visit) and since the last visit (regardless of abrocitinib treatment status*)	X	X	X	X	X	X
Concomitant (non-AD) treatment	X					
SCORAD	X	X	X	X	X	X

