Smoking history and current smoking status	Baseline characteristics, potential confounder	Case records	Frequency analysis
Renal and/or liver impairment	Baseline characteristics	Case records	Frequency analysis
Comorbidities at baseline	Baseline characteristics, potential confounder, potential subgroup identifier	Case records	Frequency analysis
If positive anamnesis at baseline exists: Improvement of (allergic) asthma symptoms from baseline	Baseline characteristics, potential confounder, potential subgroup identifier	Case records	Frequency analysis
If positive anamnesis at baseline exists: Improvement of (allergic) rhinitis symptoms from baseline	Baseline characteristics, potential confounder, potential subgroup identifier	Case records	Frequency analysis
If positive anamnesis at baseline exists: Improvement of polyposis nasi symptoms from baseline	Baseline characteristics, potential confounder, potential subgroup identifier	Case records	Frequency analysis
If positive anamnesis at baseline exists: Improvement of alopecia areata from baseline Baseline characteristics, potential confounder, potential subgroup identifier		Case records	Frequency analysis

If positive anamnesis at baseline exists: Improvement of chronic hand eczema symptoms from baseline	Baseline characteristics, potential confounder, potential subgroup identifier	Case records	Frequency analysis
If positive anamnesis at baseline exists: Improvement of prurigo nodularis symptoms from baseline	Baseline characteristics, potential confounder, potential subgroup identifier	Case records	Frequency analysis
Previous treatments for diagnosed AD	Baseline characteristics, potential confounder, potential subgroup identifier	Case records	Frequency analysis
Concomitant treatment of AD (and dosage)	Baseline characteristics, Exposure, explorative outcome, potential confounder, potential subgroup identifier	Case records	Frequency analysis and Summary statistics (n, mean, median, standard deviation, minimum and maximum) for dose
Concomitant (non-AD) treatment	Baseline characteristics, outcome, potential confounder, potential subgroup identifier	Case records	Frequency analysis with respect to level 1 and level 2 of ATC codes
Dosage of abrocitinib used	Exposure, potential confounder, explorative outcome variable, potential subgroup identifier	Case records	Summary statistics (n, mean, median, standard deviation, minimum and maximum)

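### Comorbidity improvement is defined as improvement on abrocitinib but scheduled as one Month 12 rating against baseline, so for patients who stopped or switched earlier the table can answer a different question

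*Protocol*

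**What the plan says.** **Definition.** Protocol 9.1.1, patient characteristics item c, makes the rating conditional: "If baseline visit had a positive anamnesis for the following", followed by asthma, rhinitis, polyposis nasi, chronic hand eczema, prurigo nodularis and alopecia areata. The outcome is the "assessment of investigator if comorbidity improves during abrocitinib therapy". The list heading says items are taken at baseline only, "except for c., f., g., and h. with additional assessment at subsequent visits".

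**Schedule.** Protocol 9.2.3.2, Table 1, gives each of the six rows a single mark, at Month 12. The row wording is of the form "If positive anamnesis at baseline exists: Improvement of asthma symptoms from baseline". SAP 1.1, Table 1, does the same, for example "If positive anamnesis at baseline exists: Improvement of allergic rhinitis symptoms from baseline".

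**Analysis.** SAP 6.3 lists the items, for example "If positive anamnesis at baseline exists: Improvement of (allergic) asthma symptoms from baseline", with a frequency analysis as the whole operational definition. The closing sentence of SAP 8.2.3 assigns all 6.3 endpoints to the FAS and all subgroups. The FAS (SAP 5.1) requires at least one dose, not continued treatment.

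**Follow-up.** Protocol 7.4, 9.1 and 10.3 keep patients under observation for 12 months after they stop or switch. Protocol 9.2.4.5 records the abrocitinib stop date and the start date of a new treatment.

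**A contrast.** Tolerability has its own rule in Protocol 9.2.4.10: "At the final visit or if a patient discontinues with abrocitinib, the healthcare professional (HCP) will be asked to assess the general tolerability".

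**The concern.** For a patient still on abrocitinib at Month 12, improvement from baseline and improvement during therapy cover much the same period. For a patient who stopped at, say, Month 3, they do not: about nine months off the drug lie between the stop and the only scheduled rating.

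The protocol's own rationale shows why this matters. Section 7.4 describes dupilumab as authorised for severe asthma and refers to type 2 inflammation "resulting in market authorization for dupilumab in the European Union for chronic rhinosinusitis with nasal polyposis"; it describes baricitinib as authorised for alopecia areata. A patient who moves to one of these may improve in the very comorbidity being rated. Conversely, a patient who improved on abrocitinib, stopped and relapsed may be rated as not improved at Month 12.

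Section 7.4 says the impact of abrocitinib-treated AD on these comorbidities is to be assessed. If the two kinds of patient are mixed in one percentage, the reported figure does not match the endpoint it is reported under.

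**Working it through.** The documents state no rate, sample size or precision for this endpoint, so there is no figure to reproduce. The check has two parts.

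**1. The texts side by side**

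| Question | Protocol 9.1.1 | Table 1 (both documents) | SAP 6.3 and 8.2.3 |
|---|---|---|---|
| Who is rated | Positive history at baseline | Same | Same; FAS |
| Reference period | Abrocitinib therapy | Since baseline | Since baseline |
| When | Subsequent visits | Month 12 only | No visit named |
| Off abrocitinib at Month 12 | Not addressed | Not addressed | Not addressed |

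Protocol 9.2.4.2 does not help: it covers comorbidities at baseline and names only flares, hospitalizations and absent days for later visits. The detailed table in SAP 8.2.3 has no row for the six items.

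**2. What the mismatch can do to the overall percentage**

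Among patients with the comorbidity at baseline, and taking all of them as rated, let

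- d = share off abrocitinib at Month 12
- p = share improved among those still on it
- q = share of the off-drug patients who improved while they were on it
- r = share of the off-drug patients rated improved from baseline at Month 12

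Figure matching the definition: T = (1 − d)p + dq. 
Figure the schedule would produce: O = (1 − d)p + dr. 
Shift: O − T = d(r − q). The rate p cancels.

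All inputs below are assumptions. With p = 50% and d = 30%:

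- q = 20%, r = 50%: T = 0.70 × 50 + 0.30 × 20 = 41%; O = 0.70 × 50 + 0.30 × 50 = 50%; shift +9 points.
- q = 50%, r = 20%: T = 50%; O = 0.70 × 50 + 0.30 × 20 = 41%; shift −9 points.
- q = r = 30%: T = O = 44%; shift 0.

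Over d = 10% to 50%:

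| d | q 20%, r 50% | q = r | q 50%, r 20% |
|---|---|---|---|
| 10% | +3 | 0 | −3 |
| 20% | +6 | 0 | −6 |
| 30% | +9 | 0 | −9 |
| 40% | +12 | 0 | −12 |
| 50% | +15 | 0 | −15 |

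If sites instead leave off-drug patients unrated, the percentage among rated patients is p and the shift is p − T = d(p − q). With p = 50%, q = 20% and d = 30% that is 50 − 41 = +9 points. Leaving them out therefore does not restore the defined quantity unless q = p.

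**The case against.** The case on the other side has real weight.

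- **Who is rated.** A reader might infer that the item is recorded in every patient regardless of treatment status. The documents do not say so. Only patients with a positive baseline history are rated, and the note extending collection to patients off abrocitinib is attached to the rows for flares, hospitalizations, absent days and topical or emollient days, not to these six. This stands; whether off-drug patients are rated is unspecified.
- **How the question is answered.** A reader might infer that a successor drug's effect is certainly credited to abrocitinib. An investigator who follows 9.1.1 could answer at Month 12 retrospectively, for the abrocitinib period only, and the eCRF question is not shown. This stands, so the claim is that it can happen. But the schedule wording points to baseline, and across about 80 sites both readings could enter one table.
- **Planned split.** SAP 5.4 has a subgroup of patients who switched from abrocitinib versus those who remain, and 6.3 endpoints are run in all subgroups. This gives part of the separation. It is labelled as dosage switchers, leaves unclear where a patient who stopped without a successor belongs, does not correct the overall FAS figure, and cannot recover improvement seen before stopping.
- **Missing ratings.** A reader might infer that patients without a Month 12 rating vanish. SAP 7 and 8.1 display missing counts, so they remain visible as missing.
- **Causality.** Protocol 9.9 already concedes that lack of a control group limits causal reading. That is true, but the point here is narrower: the tabulated quantity should be the one defined.

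**Conclusion.** The mismatch is real: one endpoint has two reference periods and two timings, and there is no rule for patients off abrocitinib at Month 12. Following the plan as written can therefore give a percentage that does not match the plan's own definition.

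Neither the size nor the direction can be determined from the documents. It depends on d, q and r, none of which is given; the 3 to 15 points either way rest on the assumed d of 10% to 50% and a 30-point gap between q and r, and the shift is zero if q = r.

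A reader might be tempted to measure the error against the rate in patients still on the drug: with 30% off drug and 40% improving among those still on it, 0.70 × 40 + 0.30 × 60 = 46% would look like +6 points, and 0.70 × 40 + 0.30 × 10 = 31% like −9. That comparison silently sets q = 40% for patients who stopped. If q equals the assumed r in each case, the shift is zero.

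The endpoint is explorative and the study descriptive. Primary and secondary results are not touched. The change is worth making because the section 7.4 aim rests on these items and the remedy is small.

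**What to change.** 1. **Reconcile the texts.** Bring Protocol 9.1.1, Table 1 in both documents and SAP 6.3 to one definition, stating that the reference period is the time on abrocitinib and at which visits the items are rated.
2. **Add one reading.** Show the existing six items also at the visit where abrocitinib discontinuation is documented, as 9.2.4.10 does for tolerability. Word them for the period up to the stop date, because that visit may come after a new treatment has begun (9.2.4.5). Use this reading for patients who stopped, and the Month 12 reading for those still on the drug.
3. **Tabulate by exposure.** In SAP 6.3, also report the Month 12 rating by treatment status at assessment (on abrocitinib, off without another systemic, on another systemic), derived from the recorded stop and start dates, with the number missing in each.

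Do not report the still-on-abrocitinib stratum alone as the endpoint. It selects patients who stayed on the drug, and would overstate improvement if those who respond and tolerate it are the ones who stay.

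**Cost.** Item 3 needs SAP wording only. Items 1 and 2 need a change to protocol text and Table 1, and one existing eCRF item shown at one more visit for patients who stop; no extra procedure. The strata will be small. For any patient whose discontinuation visit precedes the change, only a retrospective Month 12 answer will exist, and the table should say how many there are.
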